6.6 Evaluation of Toxicity

All registered patients will be evaluated for toxicity probably related to the treatment. There have been no reported toxicities directly attributed to intraoral or extraoral LLLT. No systemic toxicities (e.g fever, nausea, fatigue) are anticipated or have been reported in association with oral LLLT. No specific toxicity is expected attributable to LLLT due to the addition of LLLT in patients receiving radiation with concurrent chemotherapy. Toxicity data will be collected at least weekly during the course of treatment to ensure the validity of this claim.

6.7 Specific Toxic Outcomes

No toxicities or dose-limiting toxicities have been reported in association with LLLT in the biomedical literature. Specifically with respect to LLLT for the prevention and/or management of oral mucositis, no toxicities or DLTs have been reported. Any toxicities arising would be anticipated to be localized to the exposed tissues. These would include undesignated skin/mucosal changes, such as localized skin erythema, mucosal swelling (not typically associated with mucositis) or unanticipated sensory changes. Of note, oral mucositis may develop despite LLLT and will not be considered a treatment-related toxicity.

We will closely monitor the following outcomes: grade 3 oral dysesthesia (burning/tingling sensation in the distribution exposed to LLLT), grade 3 or 4 oral mucosal swelling not attributable to mucositis (GI Disorders, other, specify), Grade 3 erythema and/or pain of the skin (in the distribution exposed to LLLT), visual loss, blurred vision, retinal tear or detachment, uveitis, or other eye disorders. If 2 or more patients out of the first 10 (or fewer) treated in the phase II portion of the study develop a grade III (using the CTCAE guidelines) or higher toxicity in any of these categories that are probably or definitely related to the LLLT treatment received within the first 2 weeks after the completion of treatment, we would recommend revisiting the study for safety reasons. Adjudication is necessary to ensure that we judge this study based on adverse events that are specific to LLLT therapy and not any other therapy that the patient happens to receive. We will continue to monitor these specific toxic outcomes throughout the course of the trial, in a sliding window fashion.

6.8 Other toxic outcomes

Data on other toxic side effects (excluding those detailed in the previous paragraph) that patients may experience will also be collected. We have chosen a safety threshold of 0.25 to monitor other toxic side effects. We would recommend termination of the phase II portion of the study for safety reasons if there were X many occurrences of grade 3 or higher toxicity (using the CTCAE guidelines) among the first N (or fewer) patients treated, as it would result in an upper confidence limit greater than 0.25:

N	X	p	UCL
8	1	0.125	0.255
13	2	0.154	0.256
18	3	0.167	0.253
22	4	0.181	0.261
27	5	0.185	0.256
32	6	0.188	0.252
36	7	0.194	0.256
41	8	0.185	0.252

In the above table, N = the number of patients treated; X = the cumulative number of patients with a grade 3 or higher toxicity currently observed; p = the observed toxicity rate; and UCL = the exact 1-sided upper 80% confidence limit for p, using Wilson's method without a continuity correction. After treating 41 patients, the potential toxicity risk of this regimen should be well defined, and thereafter the possible need for termination of the study based on toxicity should be minimal.

6.9 Expected accrual rate, accrual duration, and study duration

Our anticipated accrual rate at our center is 25 patients per year. The accrual rate per year at UPMC will also be 25 patients per year. Thus, it should take approximately 1 year to accrue the maximum 50 patients needed for the data analysis. Allowing for 2 weeks of follow-up to obtain the primary endpoint on the last patient enrolled and 4 months to assemble, analyze and interpret the data the total study duration is projected to be at most 1.5 years.

7.0 Adverse Events and Safety Monitoring

There have been no reported toxicities directly attributed to oral LLLT for the prevention/management of mucositis. Any toxicity would be expected to be localized to the region exposed (e.g. erythema of the skin, hyperalgesia). We do not anticipate treatment-related toxicity. LLLT has never been demonstrated to exacerbate or potentiate mucositis. Regardless, subjects will be followed carefully for any possible toxicity. Adverse event (AE) monitoring and reporting is a routine part of every clinical trial. These will be followed per WSU IRB requirements.

7.1 Reporting of Serious Treatment Emergent Adverse Events

An adverse event for the purposes of this protocol is the appearance of (or worsening of any pre-existing) undesirable sign(s), symptom(s), or medical condition(s) occurring after signing the informed consent even if the event is not considered to be related to the study intervention. Please refer to the adverse event section of the protocol for the protocol-specific definitions of study drug and study treatment.

The descriptions and grading scales found in the revised NCI CTCAE version 4.0 will be utilized for AE reporting. All appropriate treatment areas should have access to a copy of the CTCAE version 4.0. A copy of the CTCAE version 4.0 can be downloaded from the CTEP web site http://ctep.cancer.gov/protocolDevelopment/electronic_applications/ctc.htm.

If CTCAE grading does not exist for an adverse event, the severity of mild, moderate, severe, and life-threatening, or grades 1 - 4, will be used. Adverse event monitoring should be continued for at least 3 months following the last LLLT treatment.

- **‘Expectedness’:** AEs can be ‘Unexpected’ or ‘Expected’ for expedited reporting purposes only.
- **Attribution** of the AE:
 - Definite – The AE is *clearly related* to the study treatment.
 - Probable – The AE is *likely related* to the study treatment.
 - Possible – The AE *may be related* to the study treatment.
 - Unlikely – The AE is *doubtfully related* to the study treatment.
 - Unrelated – The AE is *clearly NOT related* to the study treatment.

Adverse events (but not serious adverse events) occurring before starting study treatment but after signing the informed consent form will be recorded as part of the medical history or current medical condition. Abnormal laboratory values or test results constitute adverse events only if they induce clinical signs or symptoms, are considered clinically significant or require therapy (e.g., any hematologic abnormality that requires transfusion or cytokine treatment); and should be recorded on the Adverse Events Case Report Form (CRF) under the signs, symptoms or diagnosis associated with them. In addition, isolated abnormal laboratory values that are considered clinically significant (e.g., cause study discontinuation or constitutes in and of itself a Serious Adverse Event) should be recorded on the Adverse Events CRF. SAEs occurring after signing the Informed Consent are recorded on the Adverse Event CRF.

7.2 AdverseEventCharacteristics

The occurrence of adverse events should be sought by non-directive questioning of the patient at each visit during the study. Adverse events also may be detected when they are volunteered by the patient during or between visits or through physical examination, laboratory test, or other assessments. As far as possible, each adverse event should be evaluated to determine:

1. The severity grade (CTCAE grade 1-4)
2. Its relationship to each study treatment (suspected/not suspected)
3. Its duration (start and end dates or if continuing at final exam)
4. Action taken (no action taken/temporarily interrupted; study treatment permanently discontinued due to this adverse event; concomitant medication taken; non-drug therapy given; hospitalization/prolonged hospitalization)
5. Whether it is serious, where a serious adverse event (SAE) is defined as one which:
 - Is fatal or life-threatening
 - Results in persistent or significant disability/incapacity
 - Constitutes a congenital anomaly/birth defect
 - Requires inpatient hospitalization or prolongation of existing hospitalization, unless hospitalization is for:
 - Routine treatment or monitoring of the studied indication, not associated with any deterioration in condition (specify what this includes)

- Elective or pre-planned treatment for a pre-existing condition that is unrelated to the indication under study and has not worsened since signing the informed consent
- Treatment on an emergency outpatient basis for an event not fulfilling any of the definitions of a SAE given above and not resulting in hospital admission
- Social reasons and respite care in the absence of any deterioration in the patient's general condition
- Is medically significant, i.e., defined as an event that jeopardizes the patient or may require medical or surgical intervention to prevent one of the outcomes listed above

Unlike routine safety assessments, SAEs are monitored continuously and have special reporting requirements; see protocol section on Serious Adverse Event reporting.

All adverse events should be treated appropriately. Once an adverse event is detected, it should be followed until its resolution, an assessment should be made at each visit (or more frequently, if necessary) of any changes in its severity, its suspected relationship to the study treatment, any of the interventions required to treat it, and its outcome.

Information about all serious adverse events will be collected and recorded. A serious adverse event is an undesirable sign, symptom or medical condition which:

- is fatal or life-threatening
- results in persistent or significant disability/incapacity
- constitutes a congenital anomaly/birth defect
- requires inpatient hospitalization or prolongation of existing hospitalization, unless hospitalization is for:
 - routine treatment or monitoring of the studied indication, not associated with any deterioration in condition (specify what this includes)
 - elective or pre-planned treatment for a pre-existing condition that is unrelated to the indication under study and has not worsened since the start of study drug
 - treatment on an emergency outpatient basis for an event not fulfilling any of the definitions of a SAE given above and not resulting in hospital admission
 - social reasons and respite care in the absence of any deterioration in the patient's general condition
- is medically significant, i.e., defined as an event that jeopardizes the patient or may require medical or surgical intervention to prevent one of the outcomes listed above

Events **not** considered to be serious adverse events are hospitalizations for the routine treatment or monitoring of the studied indication, not associated with any deterioration in condition.

- Sores in the mouth and throat that are likely to interfere with swallowing
- Temporary hair loss (of the face/chin/neck)
- Tanning, redness, or blistering or peeling of skin in treatment area
- Loss of teeth, or cavities in teeth, if strict dental care is not followed
- Hardness and tightness of the skin and muscles of the head and neck
- Dryness of the mouth or altered taste that may be permanent
- Loss of appetite

- Weight loss which may necessitate the placement of a temporary feeding tube
- Nausea and/or vomiting
- Weakness
- Hearing loss, ringing of the ears
- Numbness of the fingers and toes
- Lower blood counts with risk of infection or bleeding
- Anemia
- Loss of taste
- Muscle cramps
- Loss of coordination
- Involuntary movement
- Restlessness
- Treatment, which was elective or pre-planned, for a pre-existing condition that did not worsen
- Treatment on an emergency, outpatient basis for an event **not** fulfilling any of the definitions of serious given above and **not** resulting in hospital admission.

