2.0 Introduction

2.1 DiseaseOverview

Combined modality therapy with chemotherapy and radiation is a commonly employed treatment approach for patients with various types of HNC [1]. Despite the overall safety and efficacy of this treatment modality, side effects exist, including acute chemoradiation-induced pain, dermatitis, xerostomia, dysgeusia, dysphagia, odynophagia, and oral mucositis. In fact, a majority of patients treated with this modality will experience some degree of oral mucositis (OM) [2]. OM can affect many oral functions including mastication and swallowing which may lead to dehydration, renal failure and necessitate the placement and use of a feeding tube and negatively impact and patient's quality of life (QOL). Severe OM can also predispose a patient to increased risk of infections requiring hospitalization and increased cost of treatment [3]. The severity of these reactions can be so severe that patients who experience treatment-related mucositis are less likely to complete the planned course of therapy without unplanned interruptions in therapy. Previous studies provide evidence that unplanned breaks in radiotherapy for HNC result in worse tumor control [4]. Furthermore, adverse events can increase the cost of healthcare by resulting in preventable hospital admissions for intravenous hydration and nutritional support and procedures including feeding tube placement. In fact, OM has

been shown to be associated with an incremental cost of \$1,700 - \$6,000 per patient, depending on the grade [5].

Despite multiple clinical trials, no single treatment has been proven to be effective in substantially reducing incidence or severity of chemoradiation induced oral mucositis. The current standard practice for the management of OM is symptom management and supportive care with narcotic pain medications and anesthetic mouth rinses and nutritional support with supplementation either by mouth or feeding tube.

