7.3 WSUIRBAdverseEventreporting

All adverse event reporting will be done in compliance with the Wayne State Institutional Review Board as follows:

A. Death or Life Threatening Adverse Reaction or Unexpected Event:

If a death or immediately life-threatening Adverse Reaction/Unexpected Event occurs, it must be reported to the IRB office within three (3) business days of the PI becoming aware, even if the information in the report is incomplete. As more information is forthcoming, one or more additional reports should be filed with the IRB. The initial report of the Adverse Reaction or Unexpected Event and follow-up reports should be filed using the IRB Adverse Reaction and Unexpected Event Form.

B. Serious Adverse Reaction or Unexpected Event:

If a Serious Adverse Reaction/Unexpected Event occurs (one that necessitates or prolongs hospitalization, results in a permanent or significant disability or congenital anomaly, or is judged to be serious by the principal investigator), and is **unexpected**, (not listed in the consent form) it must be reported to the IRB within five (5) business days of the PI becoming aware. If the Serious Adverse Event **is** listed in the consent form but a relationship to the study intervention/activity **cannotberuledoutbythePI**, it must be reported to the IRB within five (5) business days. If the information is incomplete on the initial filing, follow-up reporting is required. The IRB Adverse Reaction and Unexpected Event Form should be used in all reports pertaining to these reactions/events.

C. Non-Serious (Moderate or Minor) Adverse Reaction or Unexpected Event:

If a non-serious Adverse Reaction occurs that is **unexpected** (not listed in the informed consent), it must be reported to the IRB within ten (10) business days of awareness, **unless the Principal Investigator can rule out the relationship to the study agent or intervention**. If a non-serious Adverse Reaction occurs that is **expected** (listed in the informed consent), but is more frequent,

more intense or longer lasting than expected, or requires medical treatment, it must be reported to the IRB within ten (10) business days. If the reaction that is listed in the consent form occurs as described in the informed consent, **it does not need to be reported to the IRB**.

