If an Unexpected Event occurs, it must be reported to the IRB within ten (10) business days of the awareness by the Principal Investigator. The Adverse Reaction/ Unexpected Event Form should be used for these submissions.

D. Possibly-Related Adverse Reactions/ Unexpected Events

In the rare case where a sponsor requires that a non-reportable (i.e., possibly related) Adverse Reaction/ Unexpected Event be reported to the IRB, an amendment should be submitted by the PI requesting that the non-reportable safety report be appended to the IRB file. It remains the primary responsibility of the WSU PI, the study sponsor, and any associated DSMB to identify trends that might require the event to be elevated to definitely or probably related status.

If a trend is identified that elevates the Adverse Reaction to definitely or probably related status, an Adverse Reaction/ Unexpected Event Form should be completed, along with an amendment for consent form changes, if needed, and submitted to the IRB.

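### Sections 7.2 and 7.3 contradict their own rules: listed toxicities are called not serious with no exception for cases meeting a seriousness criterion, and possibly related events are called non-reportable

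*Combined protocol and SAP*

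**What the plan says.** Section 7.2 gives the definition of a serious adverse event twice. An event is serious if it "is fatal or life-threatening", disables, is a congenital anomaly, or "requires inpatient hospitalization or prolongation of existing hospitalization, unless hospitalization is for" one of four narrow reasons. It is also serious if it "is medically significant, i.e., defined as an event that jeopardizes the patient or may require medical or surgical intervention" to prevent one of those outcomes.

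Directly after this, Section 7.2 states what is not serious. The lead-in names "hospitalizations for the routine treatment or monitoring of the studied indication, not associated with any deterioration in condition". A bulleted list of toxicities follows. It opens with "Sores in the mouth and throat that are likely to interfere with swallowing" and goes on to weight loss that may lead to a temporary feeding tube, nausea or vomiting, hearing loss, possibly permanent dry mouth, and lower blood counts with a risk of infection or bleeding. The last two bullets (elective or pre-planned treatment, and emergency outpatient treatment) carry limits of their own. The toxicity bullets carry none that refers to the seriousness criteria.

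Section 7.3 sets out reporting to the Wayne State IRB:

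- Part A covers deaths and life-threatening events and sets no condition on attribution.
- Part B covers serious events that are unexpected. It also covers those "listed in the consent form but a relationship to the study intervention/activity" cannot be ruled out by the investigator.
- Part C covers unexpected non-serious reactions unless a relationship is ruled out.
- Part D speaks of an event that is "non-reportable (i.e., possibly related"), and links use of the report form to a trend that raises the event to probable or definite.

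Section 7.1 defines the attribution level Possible as an event that may be related.

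**The concern.** Whoever classifies an event needs one answer to each of two questions: is it serious, and does it go to the IRB? For a foreseeable group of events the protocol gives two answers to each.

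The events are foreseeable on the protocol's own account. Section 2.1 says that "Severe OM can also predispose a patient to increased risk of infections requiring hospitalization" and also describes admissions for hydration and nutritional support. Section 5.2 grades oral mucositis up to life-threatening (CTCAE grade 4) and death (grade 5).

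At stake is the consistency of serious-event forms and of expedited IRB reports. The same protocol is opened separately at two institutions and the data are pooled, so two sites could classify the same admission differently. So could two coordinators at one site.

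**Working it through.** No arithmetic applies. The check sets the rules side by side and runs concrete cases through them.

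**Check 1: the definition in 7.2 against the list in 7.2.** The list column takes the bullets as written.

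| Case | Definition | List |
|---|---|---|
| Inpatient admission for mouth sores, with deterioration | Serious (hospitalization) | Not serious |
| Grade 4 oral mucositis | Serious (life-threatening) | Not serious |
| Grade 5 oral mucositis | Serious (fatal) | Not serious |
| Inpatient admission for low blood counts, with deterioration | Serious (hospitalization) | Not serious |
| Weight loss leading to a feeding tube | Arguably serious (medical significance) | Not serious |
| Grade 3 oral mucositis, no admission and no other criterion met | Not serious | Not serious |

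The first four rows conflict, the fifth is open to dispute, and the sixth does not conflict. The problem therefore lies with listed events that also meet a seriousness criterion, not with severe mucositis as such.

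**Check 2: 7.3 D against 7.3 A to C, for an event attributed as Possible.** Under 7.1 such an event may be related, so a relationship has not been ruled out.

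| Event judged possibly related | Parts A to C | Part D |
|---|---|---|
| Death or immediately life-threatening | A: three business days, no attribution condition | Non-reportable |
| Serious, not in the consent form | B: five business days | Non-reportable |
| Serious, in the consent form | B: five business days, since not ruled out | Non-reportable |
| Non-serious reaction, not in the consent form | C: ten business days, since not ruled out | Non-reportable |

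All four rows conflict. The monitoring report form in Appendix 11.9 asks for a yes or no on IRB reportability, which A to C and D would fill in oppositely. Section 7.2 adds a two-level scale (suspected or not suspected) and does not say where Possible falls on it.

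**Check 3: what still catches these events.** Under Section 7.4 the monitoring committee reviews two things each month: serious-event forms and study-specific monitoring reports. The report form in Appendix 11.9 calls for every grade 3, 4 and 5 event, with grade and attribution, whether or not it is classed as serious. Sections 7.3 A and B also carry their own tests (death, threat to life, hospitalization, disability, the investigator's judgement), so IRB reporting does not depend on the 7.2 list alone.

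**The case against.** The strongest reply on 7.2 is that the lead-in governs the list. It repeats the exception for routine care without deterioration, and in the definition that exception carries an unfilled instruction to specify what it includes. The bullets may be meant to fill that gap, in which case an admission with deterioration stays serious. This reading is reasonable, and it shows the text to be ambiguous rather than plainly wrong. It does not remove the conflict. The bullets name new or worsening toxicities, which sit badly under a condition of no deterioration. Because the lead-in is about hospitalizations, admitted cases are the ones it would exempt. The final bullet, on emergency outpatient treatment, does refer back to the seriousness definitions, so the same limit could have been written for the others.

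On 7.3 D, the reply is that it describes a residual class in a rare situation. Part C does leave some events unreported, for example an expected non-serious reaction that runs as the consent form describes. That may well be the intent, but the wording equates possibly related with non-reportable and sets no such limit.

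Three stronger inferences are tempting, and the documents do not support them:

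- *Admissions for mucositis may never reach the monitoring committee.* The monthly report of all grade 3 to 5 events goes to the committee whatever the seriousness class.
- *Section 6.7 lets worsening mucositis escape notice, because it does not count mucositis as treatment-related toxicity.* Mucositis is the primary endpoint, is graded weekly on two scales, and appears in the monthly report at grade 3 and above.
- *Ten to twenty of the 50 patients are affected.* That is the assumed severe mucositis rate applied to the sample (0.20 × 50 = 10; 0.40 × 50 = 20). It does not count misclassified events; grade 3 cases meeting no seriousness criterion involve no conflict.

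Section 2.1 also needs care: the admissions it ties to severe mucositis are for infection, and infection itself is not on the 7.2 list. Its mention of admissions for hydration and nutritional support is closer to the listed events.

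**Conclusion.** Both contradictions are in the text and should be corrected. A site that follows the 7.2 list as written could omit a serious-event form that the definition requires. A site that follows 7.3 D as written could omit an IRB report that A, B or C requires. The consequence is inconsistent classification and expedited reporting, not loss of severe events from oversight.

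The size cannot be stated: the documents give neither the share of patients admitted nor the share of events attributed as Possible. Nothing here affects the primary endpoint, the sample size or the decision rule.

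The conclusion assumes that staff apply the list and Part D literally. The between-site part assumes that the second institution's copy has the same wording. The protocol calls it the same protocol, but 7.3 is written for the Wayne State IRB, and the second site's reporting rules are not shown.

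**What to change.** In 7.2, add to the list of events not considered serious: *unless the event meets any seriousness criterion above*.

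In 7.3, reconcile Part D with Parts A to C so that an event attributed as Possible under 7.1 is handled one way. One option is to limit D to events not already reportable under A, B or C. Since 7.3 presents institutional procedure, the wording should be confirmed with the IRB.

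The change is two sentences of reporting text, plus a few more serious-event forms and IRB reports. Treatment, assessments, sample size and analysis stay as they are.
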